13 METHODS OF EFFICACY ANALYSES

13.1 Primary Efficacy Analysis

The primary efficacy endpoint is the change from Baseline to Week 12 in the CMAI total score. The primary endpoint will be summarized based on the Full Analysis Set.

The CMAI total score will be summarized using the Mixed Model Repeated Measures (MMRM) in the Full Analysis Set. The dependent variable will be the change from Baseline in the CMAI total score. The independent variables in the model will include the following: treatment group (pimavanserin 34 mg, pimavanserin 20 mg, or placebo), visit (Weeks 2, 4, 8, and 12), the treatment-by-visit interaction, the Baseline CMAI total score, the Baseline-by-visit interaction, and geographic region (North America, Europe, or Rest of World). An unstructured covariance matrix will be used and the Kenward-Roger approximation will be used to adjust the denominator degrees of freedom. Observed cases will be used in the model and the least squares (LS) means will be estimated using observed margins.

Sample SAS® code for the MMRM:

In the event that the model fails to converge using the unstructured covariance matrix, then the following covariance structures will be modeled in the order given (i.e. from least parsimonious to most parsimonious): heterogeneous Toeplitz, heterogeneous compound symmetry, heterogeneous autoregressive(1), Toeplitz, variance components, compound symmetry, autoregressive(1). The first covariance structure that allows for convergence will be selected for the final model.

At each visit, the effect size (Cohen's d) for the change from Baseline between the treatment groups (each pimavanserin group versus placebo group) will be calculated using the following formula:

$$\text{Effect size} = \frac{\text{LS mean difference}}{\sqrt{\text{variance}}}$$

The variance at a given visit will be obtained from the covariance matrix estimated for the MMRM model. The sign (+ or -) of the effect size will be chosen so that an effect size favoring pimavanserin will be reported as a positive number and an effect size favoring placebo will be reported as a negative number.

Summary statistics for the CMAI total score (observed and change from Baseline) will be presented for all visits from Baseline through Week 12. For change from Baseline values at each post-Baseline visit, LS means and standard errors (SE), the between-group difference in LS means with the corresponding 95% confidence interval and effect size will also be presented. In addition, LS mean \pm SE over time for the change from Baseline values by treatment group will also be presented in line plots.

The MMRM summary as described above will also be repeated in the Per-protocol Analysis Set.

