12 EFFICACY ANALYSES

All efficacy summaries will be performed using the planned treatment assignments based on the randomization schedule. No hypothesis testing is planned. Descriptive summaries of all efficacy endpoints will be provided. The summaries based on mixed model for repeated measures (MMRM) or analysis of covariance (ANCOVA) will include point estimates and confidence intervals.

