12.3 Handling of Missing Data

The primary efficacy variable will be summarized assuming missing at random using an MMRM method. Total scores that are missing, after any imputation of individual missing items as described in [Section 5.2.1](#), will not be imputed.

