13.3 Exploratory Efficacy Analyses

The Exploratory efficacy endpoints include the following:

- mADCS-CGIC agitation score
- Change from Baseline in NPI-C combined agitation and aggression domain scores
- Change from Baseline in NPI-C individual agitation and aggression domain scores

- Change from Baseline to Week 12 in the ADCS-ADL score
- Change from Baseline to Week 12 in NPI-C total score
- Change from Baseline to Week 12 in NPI-C sleep disorders domain score
- Change from Baseline to Week 12 in NPI-C combined delusions and hallucinations domain scores
- Change from Baseline to Week 12 in NPI-C combined dysphoria and apathy/indifference domain scores
- Change from Baseline to Week 12 in individual NPI-C domain scores (other than agitation, aggression and sleep disorders)
- Change from Baseline in CMAI subscale scores
- Change from Baseline in KSS score
- Change from Baseline in the MMSE score
- The proportion of subjects taking any rescue medication

The mADCS-CGIC agitation score at each timepoint will be summarized using an MMRM model with effects for treatment group (pimavanserin 34 mg, pimavanserin 20 mg, or placebo), visit (Week 2, Week 4, Week 8, and Week 12), the treatment-by-visit interaction, and geographic region (North America, Europe, or Rest of World). There is no Baseline value to include in the model. An unstructured covariance matrix will be used and the Kenward-Roger approximation will be used to adjust the denominator degrees of freedom. Observed cases will be used in the model and the LS means will be estimated using observed margins.

The change from Baseline to each post-Baseline timepoint in the NPI-C combined agitation and aggression domain scores, NPI-C individual agitation and aggression domain scores, CMAI subscale scores, and KSS will be summarized using an MMRM model similar to that described above for the primary endpoint in [Section 13.1](#), except that the Baseline value of the endpoint being summarized will be included in the model instead of the Baseline CMAI total score.

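### SAP 13.1 lists variance components (zero within-subject correlation) before compound symmetry and AR(1) in a first-to-converge fallback list, so those two cannot in practice be selected

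*SAP*

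**What the plan says.** SAP 13.1 fits change from baseline in CMAI total score at Weeks 2, 4, 8 and 12 with an unstructured covariance matrix and Kenward-Roger degrees of freedom. Besides treatment, visit and their interaction, the model includes "the Baseline CMAI total score, the Baseline-by-visit interaction, and geographic region". If it does not converge, seven alternatives are tried in this order: "heterogeneous Toeplitz, heterogeneous compound symmetry, heterogeneous autoregressive(1), Toeplitz, variance components, compound symmetry, autoregressive(1". The SAP describes that order as "i.e. from least parsimonious to most parsimonious" and adds: "The first covariance structure that allows for convergence will be selected for the final model". No information criterion or other comparison enters the choice.

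On missing data, SAP 12.3 states: "The primary efficacy variable will be summarized assuming missing at random using an MMRM method". Total scores still missing after item-level imputation are not imputed.

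SAP 12 and 13.1 make the model estimates the reported result, including "LS means and standard errors (SE), the between-group difference in LS means with the corresponding 95% confidence interval". SAP 12.4 plans no hypothesis testing. The SAP does not define variance components, and the sample SAS code is not visible in the public text.

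**The concern.** A list governed by the first structure to converge works only if each entry can fail while a later one succeeds. Variance components is fifth of the seven fallbacks, and it can hardly fail. Compound symmetry and AR(1) stand behind it, although both keep within-subject correlation and variance components does not.

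That correlation is what lets an MMRM use a dropout's earlier post-baseline scores when it estimates Week 12. The list therefore prefers the one structure that drops the mechanism SAP 12.3 relies on over two that keep it.

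At stake are the LS means, between-group differences and 95% confidence intervals for CMAI. The same model is repeated in the Per-protocol set. Similar models are specified for ZBI (13.2) and for NPI-C agitation and aggression, CMAI subscales, KSS and MMSE (13.3).

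**Working it through.** **1. Parameter counts.** With t visits (4 for CMAI, 3 for MMSE), in the SAP's order:

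| Structure | Formula | t = 4 | t = 3 |
|---|---|---|---|
| Unstructured (UN) | t(t+1)/2 | 10 | 6 |
| Heterogeneous Toeplitz | 2t−1 | 7 | 5 |
| Heterogeneous CS | t+1 | 5 | 4 |
| Heterogeneous AR(1) | t+1 | 5 | 4 |
| Toeplitz | t | 4 | 3 |
| Variance components (VC) | 1, or t if one per visit | 1 or 4 | 1 or 3 |
| Compound symmetry (CS) | 2 | 2 | 2 |
| AR(1) | 2 | 2 | 2 |

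On the one-variance reading the fallbacks run 7, 5, 5, 4, 1, 2, 2, so the stated ordering is false. On the per-visit reading they run 7, 5, 5, 4, 4, 2, 2 and it holds. All off-diagonal terms are zero on both readings.

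**2. Reachability.** With one variance, the REML estimate is closed form: residual sum of squares divided by residual degrees of freedom. It fails only on degenerate data. CS and AR(1) contain this model at correlation 0, so they would be expected to fail there too. With one variance per visit the fit is weighted least squares. In simulated data VC converged in every fit on both readings, with 111 subjects (300 datasets) and with 30 (200 datasets).

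**3. Effect on missing data.** For a subject who drops out, the model's implied Week 12 value is x₁₂'β + V₁₂,obs V_obs⁻¹ (y_obs − X_obs β). Under VC, V₁₂,obs = 0, so the second term vanishes and earlier visits contribute nothing. Because treatment and baseline both interact with visit, the Week 12 estimate becomes an ANCOVA on subjects observed at Week 12, linked to other visits only through the common region term.

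**4. Size, first illustration.** The documents give no SDs, correlations or dropout rates, so these are assumed: correlation 0.75 per 4 weeks including baseline; SDs rising 12-14-16-18 (baseline 12) or constant at 16; true Week 12 difference −5. Dropout after Weeks 2, 4 and 8 is logistic, with slope 1.5 per SD of the last observed score (0 in scenario C). The mean model is the SAP's, and VC is fitted with one variance. Bias in the Week 12 difference at 17% placebo dropout (rising SDs / constant SD; positive means benefit understated; 20,000 per arm, 12 replicates, Monte Carlo SE 0.04 to 0.06):

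| Dropout | VC | CS | AR(1) | UN |
|---|---|---|---|---|
| A: score-dependent, placebo only | +1.2 / +1.0 | +0.6 / +0.3 | +0.4 / +0.2 | 0.0 / 0.0 |
| B: same rule in all arms (14% active) | +0.3 / +0.2 | +0.1 / +0.1 | +0.1 / 0.0 | 0.0 / 0.0 |
| C: unrelated to score | within 0.1 | within 0.1 | within 0.1 | within 0.1 |

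- Excess of VC over CS or AR(1): in A, from 1.2 − 0.6 = 0.6 to 1.2 − 0.4 = 0.8; in B, 0.1 to 0.2.
- At 10% dropout, VC bias is +0.7/+0.6 in A, +0.2/+0.1 in B and within 0.1 in C.
- If dropout follows the last change from baseline instead of the score (17%), VC bias is +1.6/+1.3 for placebo only and +0.4/+0.3 for all arms.
- Per-arm Week 12 LS means in B at 17% shift more than the difference does: VC −1.2/−1.1 in placebo and −1.0/−0.9 in active, against −0.6 to −0.2 for CS and AR(1).
- At 37 per arm (111/3; 600 replicates, SE 0.13 to 0.15), VC bias is +1.06/+0.93 in A and +0.12/+0.09 in B. The B figures cannot be told from zero.

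**5. Size, second illustration.** Different assumptions: 111 subjects, SDs 12/14/16/17, equal correlation 0.6, score-driven dropout in placebo only, true difference −5, 300 datasets.

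| Structure | Mean estimate | Bias | 95% CI coverage |
|---|---|---|---|
| UN | −5.03 | −0.03 | 94% |
| CS | −4.20 | +0.80 | 90% |
| AR(1) | −3.47 | +1.53 | 89% |
| VC | −1.68 | +3.32 | 81% (88% with per-visit variances) |

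The size of the bias, and whether CS or AR(1) does better, depend on the assumed inputs. Under score-dependent dropout VC is furthest from the truth in both illustrations.

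**The case against.** **The trigger is remote.** Unstructured and four further structures must all fail before variance components is tried. In simulated data with the first illustration's rising SDs and form of dropout, heterogeneous compound symmetry and Toeplitz each converged in 150 of 150 datasets, at 111 and at 30 subjects (general optimiser, not SAS). This stands. Neither illustration is conditioned on those failures.

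**The magnitude is assumed and often negligible.** Nothing in the documents suggests placebo-only score-dependent dropout. With 37 per arm and SD 16, the unadjusted SE of a difference is 16 × √(2/37) ≈ 3.7, so the 0.2-point excess in B is about 5% of one SE (0.2/3.7). This stands too. No test depends on the result, and observed summaries are reported alongside.

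**Variance components might mean a random subject intercept.** Its marginal covariance is compound symmetry, so correlation would not be zero. Without the SAS code this cannot be excluded, but it is a strained reading in a list of replacements for the unstructured matrix. It would also make the later compound symmetry entry redundant.

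**The ordering label may be right.** It holds if there is one variance per visit, and the SAP's own wording favours that. The ordering complaint therefore applies only to the one-variance reading. The reachability and zero-correlation points hold on both residual readings.

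**AR(1) stays behind compound symmetry after the fix.** It would remain unlikely to be reached. That harms no result, because compound symmetry keeps the within-subject correlation.

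**Reuse is by similarity.** SAP 13.2 and 13.3 refer to a similar model and do not restate the fallback order, so its carry-over to those endpoints is an inference.

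**Conclusion.** The concern holds, and it is minor. As written, the rule puts a zero-correlation structure that practically always converges ahead of two structures that retain correlation. Those two cannot in practice be selected. This follows from the text and from the form of the model, and needs no assumed input beyond reading variance components as a residual structure.

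The consequence arises only if the first five structures fail, which is unlikely in the Full Analysis Set. In the first illustration it is then an extra bias of 0.6 to 0.8 CMAI points over compound symmetry or AR(1) under placebo-only score-dependent dropout at 17%, 0.1 to 0.2 points under the same rule in all arms, and nothing material when dropout is unrelated to score. The second illustration gives a larger placebo-only figure, so these sizes are indicative only.

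**What to change.** In SAP 13.1, delete variance components, so that the fallbacks are heterogeneous Toeplitz, heterogeneous compound symmetry, heterogeneous AR(1), Toeplitz, compound symmetry and AR(1). At four visits the parameter counts are then 7, 5, 5, 4, 2, 2. The stated ordering is true and every fallback keeps within-subject correlation.

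If the sponsor wants a last resort that practically always converges, moving variance components to the end serves equally well. The SAP should then say which form is meant, because with one variance per visit the counts would end 2, 2, 4 and the ordering label would no longer hold.

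The cost is one phrase in one SAP sentence, with no new data. Protocol 9.6.1 names no covariance structure, so no protocol amendment is needed. The change should be made before database lock.

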13.2 Secondary Efficacy Analysis

The secondary efficacy endpoint is the change from Baseline to Week 12 in the ZBI total score. The secondary endpoint will be summarized using an MMRM model in the Full Analysis Set similar to that described above for the primary endpoint in [Section 13.1](#), except that the Baseline ZBI total score will be included in the MMRM model instead of the Baseline CMAI total score.

The MMRM summary as described above will also be repeated in the Per-protocol Analysis Set.

Results will be presented in summary table and line plots similar to the outputs described in Section 13.1.

13.3 Exploratory Efficacy Analyses

The Exploratory efficacy endpoints include the following:

- mADCS-CGIC agitation score
- Change from Baseline in NPI-C combined agitation and aggression domain scores
- Change from Baseline in NPI-C individual agitation and aggression domain scores

- Change from Baseline to Week 12 in the ADCS-ADL score
- Change from Baseline to Week 12 in NPI-C total score
- Change from Baseline to Week 12 in NPI-C sleep disorders domain score
- Change from Baseline to Week 12 in NPI-C combined delusions and hallucinations domain scores
- Change from Baseline to Week 12 in NPI-C combined dysphoria and apathy/indifference domain scores
- Change from Baseline to Week 12 in individual NPI-C domain scores (other than agitation, aggression and sleep disorders)
- Change from Baseline in CMAI subscale scores
- Change from Baseline in KSS score
- Change from Baseline in the MMSE score
- The proportion of subjects taking any rescue medication

The mADCS-CGIC agitation score at each timepoint will be summarized using an MMRM model with effects for treatment group (pimavanserin 34 mg, pimavanserin 20 mg, or placebo), visit (Week 2, Week 4, Week 8, and Week 12), the treatment-by-visit interaction, and geographic region (North America, Europe, or Rest of World). There is no Baseline value to include in the model. An unstructured covariance matrix will be used and the Kenward-Roger approximation will be used to adjust the denominator degrees of freedom. Observed cases will be used in the model and the LS means will be estimated using observed margins.

The change from Baseline to each post-Baseline timepoint in the NPI-C combined agitation and aggression domain scores, NPI-C individual agitation and aggression domain scores, CMAI subscale scores, and KSS will be summarized using an MMRM model similar to that described above for the primary endpoint in [Section 13.1](#), except that the Baseline value of the endpoint being summarized will be included in the model instead of the Baseline CMAI total score.

The change from Baseline to Week 12 in the ADCS-ADL and NPI-C total score, combined delusions and hallucinations, combined dysphoria and apathy/indifference and individual domain scores (except the agitation and aggression domains) will be summarized using an analysis of covariance (ANCOVA) model with effects for treatment group (pimavanserin 34 mg, pimavanserin 20 mg, or placebo) and geographic region (North America, Europe, or Rest of World) as factors, and the Baseline value of the endpoint being summarized as a covariate. Missing values will be imputed with the previous value (including Baseline) for

that subject, i.e. last observation carried forward (LOCF). In addition, an observed-case summary, ignoring missing values, will also be presented.

At Week 12, the effect size (Cohen's d) for the change from Baseline between the treatment groups (each pimavanserin group versus placebo group) will be calculated using the following formula:

$$\text{Effect size} = \frac{\text{LS mean difference}}{\sqrt{\text{MSE}}}$$

Where MSE is the mean squared error from the ANCOVA model. The sign (+ or -) of the effect size will be chosen so that an effect size favoring pimavanserin will be reported as a positive number and an effect size favoring placebo will be reported as a negative number.

The change from Baseline to each post-Baseline timepoint (Weeks 4, 8 and 12) in the MMSE will be summarized using an MMRM model in Full Analysis Set similar to that described above for the primary endpoint in [Section 13.1](#), except that the Baseline value of the MMSE will be included in the model instead of the Baseline CMAI total score. Also, the MMSE is not measured at Week 2.

Results will be presented in summary table similar to the outputs described in Section 13.1.

The use of rescue medication is determined from the Rescue Medications eCRF. The proportion of subjects taking any rescue medication during the treatment period for the Full Analysis Set will be summarized by treatment group.

Correlations among efficacy endpoints (observed cases) at Baseline (combining all 3 treatment groups) and for change from Baseline at Week 12 (combining all 3 treatment groups and by treatment group) will be assessed using Spearman's rank correlation coefficient (Spearman's rho) and presented in a correlation matrix. The 95% CIs for the Spearman's rank correlation coefficients will also be presented.

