## **9.5 Study Subjects**

### **9.5.1 Analysis Sets**

The Safety Analysis Set includes all randomized subjects who received at least 1 dose of study drug (pimavanserin or placebo). Subjects will be summarized based on the treatment which they actually received. The Safety Analysis Set will be used for all safety analyses.

The Full Analysis Set includes all randomized subjects who received at least 1 dose of study drug and who have both a baseline value and at least 1 post-baseline value for the CMAI total score. Subjects will be summarized based on their randomized treatment. The Full Analysis Set will be used for the summaries of all efficacy endpoints. The Per-protocol (PP) Analysis Set will be defined prior to unblinding the study for the final summaries. Subjects will be summarized based on their randomized treatment.

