### **9.6.3 Exploratory Endpoints**

The exploratory endpoints include the following:

- mADCS-CGIC agitation score
- Change from Baseline in NPI-C combined agitation and aggression domain scores
- Change from Baseline in NPI-C individual agitation and aggression domain scores
- Change from Baseline to Week 12 in the ADCTS-ADL score
- Change from Baseline to Week 12 in NPI-C total score
- Change from Baseline to Week 12 in NPI-C sleep disorders domain score
- Change from Baseline to Week 12 in NPI-C combined delusions and hallucinations domain scores
- Change from Baseline to Week 12 in NPI-C combined dysphoria and apathy/indifference domain scores
- Change from Baseline to Week 12 in individual NPI-C domain scores (other than agitation, aggression, and sleep disorders)

- Change from Baseline in CMAI subscale scores
- Change from Baseline in KSS score
- Change from Baseline in the MMSE score
- The proportion of subjects taking any rescue medication

The mADCS-CGIC agitation score at each timepoint will be summarized using an MMRM model with effects for treatment group (pimavanserin 34 mg, pimavanserin 20 mg, or placebo), visit (Weeks 2, 4, 8, and 12), the treatment-by-visit interaction, and geographic region (North America, Europe, or Rest of World). There is no baseline value to include in the model.

The change from baseline to each post-baseline timepoint in the NPI-C combined agitation and aggression domain scores, NPI-C individual agitation and aggression domain scores, CMAI subscale scores, and KSS will be summarized using an MMRM model similar to that described above for the primary endpoint, except that the baseline value of the endpoint being summarized will be included in the model instead of the baseline CMAI total score.

The change from baseline to Week 12 in the ADCS-ADL and NPI-C total score, combined delusions and hallucinations, combined dysphoria and apathy/indifference, and individual domain scores (except the agitation and aggression domains) will be summarized using an analysis of covariance (ANCOVA) model with effects for treatment group (pimavanserin 34 mg, pimavanserin 20 mg, or placebo), and baseline value of the endpoint being summarized, and geographic region (North America, Europe, or Rest of World).

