4 ANALYSIS SETS

Randomized Analysis Set

The Randomized Analysis Set will consist of all subjects who were randomized.

Subjects will be classified according to the randomized treatment assignment.

Safety Analysis Set

The Safety Analysis Set will consist of a subset of subjects in the Randomized Analysis Set who received at least one dose of study drug.

Subjects will be classified according to the actual treatment received.

Full Analysis Set

The Full Analysis Set will consist of a subset of subjects in the Safety Analysis Set who have both a Baseline value and at least 1 post-Baseline value for the CMAI total score.

Subjects will be classified according to the randomized treatment assignment.

Per-protocol Analysis Set

The Per-protocol Analysis Set will consist of a subset of subjects in the Full Analysis Set who do not have any protocol deviation which is considered to have substantial impact on the primary efficacy outcome, change from Baseline to Week 12 in the CMAI total score. The precise reasons for excluding subjects from the Per-protocol Analysis Set will be fully defined and documented *a priori* before the clinical database lock.

Subjects will be classified according to the randomized treatment assignment.

Pharmacokinetics Analysis Set

The Pharmacokinetics Analysis Set will consist of subjects with at least one measurable pimavanserin plasma concentration.

Subjects will be classified according to the actual treatment received.

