12.1.3 Exploratory Efficacy Variables

The exploratory efficacy endpoints include the following:

- mADCS-CGIC agitation score
- Change from Baseline in NPI-C combined agitation and aggression domain scores
- Change from Baseline in NPI-C individual agitation and aggression domain scores
- Change from Baseline to Week 12 in the ADCS-ADL score
- Change from Baseline to Week 12 in NPI-C total score

- Change from Baseline to Week 12 in NPI-C sleep disorders domain score
- Change from Baseline to Week 12 in NPI-C combined delusions and hallucinations domain scores
- Change from Baseline to Week 12 in NPI-C combined dysphoria and apathy/indifference domain scores
- Change from Baseline to Week 12 in individual NPI-C domain scores (other than agitation, aggression and sleep disorders)
- Change from Baseline in CMAI subscale scores
- Change from Baseline in KSS score
- Change from Baseline in the MMSE score
- The proportion of subjects taking any rescue medication

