12.2 Adjustment for Covariates

For continuous variables summarized using MMRM or ANCOVA, the Baseline value of the endpoint being summarized (except mADCS-CGIC) and geographic region (North America, Europe, or Rest of World) will be included as covariates as described in [Section 13](#).

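### The mADCS-CGIC repeated-measures model has no baseline severity term although Baseline CMAI exists for every analysed subject; adding it is a nearly free, low-priority improvement to an exploratory endpoint.

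*SAP*

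**What the plan says.** SAP 13.3 fits the mADCS-CGIC score with treatment group and "visit (Week 2, Week 4, Week 8, and Week 12), the treatment-by-visit interaction, and geographic region (North America, Europe, or Rest of World"). Its reason for stopping there is "There is no Baseline value to include in the model". Protocol 9.6.3 gives the same terms and the same reason ("There is no baseline value to include in the model"), and the protocol synopsis agrees.

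SAP 12.2 sets the general rule for endpoints that are analysed with a model: "the Baseline value of the endpoint being summarized (except mADCS-CGIC) and geographic region (North America, Europe, or Rest of World) will be included as covariates". The mADCS-CGIC is the only named exception.

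On data availability, SAP 4 limits the Full Analysis Set to treated subjects "who have both a Baseline value and at least 1 post-Baseline value for the CMAI total score". Protocol 9.5.1 says "The Full Analysis Set will be used for the summaries of all efficacy endpoints", which covers this one. The endpoint is exploratory (SAP 12.1.3). SAP 12 plans point estimates and confidence intervals without hypothesis tests.

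**The concern.** A covariate does not have to be the outcome's own baseline. The mADCS-CGIC rates change in agitation and aggression, and the CMAI measures agitation. For CMAI change, SAP 13.1 adjusts for Baseline CMAI and lets its effect differ by visit. Protocol 9.7 and SAP 13.4 also intend to anchor CMAI response to the clinician's global rating, so the sponsor expects the two instruments to move together.

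Nothing else planned for the mADCS-CGIC takes account of baseline severity. Randomization is stratified by region only (SAP 3.3). The responder comparison is stratified by region only (SAP 13.4). Subgroup analyses cover the primary and secondary endpoints only (SAP 12.5).

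Two things are at stake: the width of the intervals, and whether a chance difference in baseline agitation between small arms colours the clinician-rated result.

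**Working it through.** The documents give no figure to reproduce on this point. They contain no correlation between Baseline CMAI and mADCS-CGIC, so rho is an assumption and is shown over a range.

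**Inputs**
- 111 randomized (SAP 3.5), allocated 1:1:1 (SAP 3.3): about 111/3 = 37 per arm, assuming an even split.
- Two-sided 95% intervals (SAP 5.1).
- Three arms and three regions: 5 model parameters at a visit without the covariate, 6 with it.
- Assumed: complete data, a linear covariate effect, and a single-visit ANCOVA as an approximation to the per-visit MMRM contrast.

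**Step 1. Interval without the covariate.** Degrees of freedom are 111 − 5 = 106. Half-width = t(0.975, 106) × √(2/37) = about 1.983 × 0.2325 = 0.461 SD of the mADCS-CGIC score.

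**Step 2. Effect of adding Baseline CMAI.** With df = 111 − 6 = 105,

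width ratio = √[(1 − rho²) × (1 + 1/(df − 1))] × t(0.975, 105)/t(0.975, 106).

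The factor 1 + 1/104 is the price of estimating the slope; the ratio of t values is about 1.0001. At rho 0.3: √(0.91 × 1.0096) × 1.0001 = 0.959.

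| Assumed rho | Adjusted/unadjusted width | Half-width (SD) | Shift from a 0.25 SD imbalance (SD) |
|---|---|---|---|
| 0 | 1.005 | 0.463 | 0 |
| 0.1 | 1.000 | 0.461 | 0.025 |
| 0.2 | 0.985 | 0.454 | 0.050 |
| 0.3 | 0.959 | 0.442 | 0.075 |
| 0.4 | 0.921 | 0.425 | 0.100 |
| 0.5 | 0.870 | 0.401 | 0.125 |

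The break-even correlation is about √(1/105) = 0.098. With 30 per arm it is 0.109, and the width ratios at rho 0.2, 0.3 and 0.4 are 0.986, 0.960 and 0.922, so moderate loss of data changes little.

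**Step 3. Chance imbalance.** The standardized baseline difference between two arms has SD √(2/37) = 0.2325. The probability that it exceeds 0.25 in either direction is 2 × [1 − Φ(0.25/0.2325)] = 2 × [1 − Φ(1.075)] = about 28%. Given an imbalance of 0.25 SD, the unadjusted difference moves by 0.25 × rho SD (last column). At rho 0.3 that is 0.075/0.461, or about 16% of the half-width.

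**Step 4. Simulation check.** A single-visit model with 37 per arm, three regions and 4,000 runs per value of rho gave width ratios of 1.005, 1.000, 0.985, 0.958 and 0.869 at rho 0, 0.1, 0.2, 0.3 and 0.5. The unadjusted estimator was unbiased on average, and its intervals missed the true value in 4.4% to 5.2% of runs.

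**The case against.** The omission is deliberate, explained and the same in protocol and SAP. The rule in SAP 12.2 is to adjust each endpoint for its own baseline, and this scale has none, so the exception is not an inconsistency. The sentence in SAP 13.3 speaks of the scale's own baseline and does not deny that other severity measures exist. The rating is already made relative to the Baseline interview (SAP 5.2.5), so its remaining correlation with baseline severity may be weak and of either sign. Baseline CMAI and NPI-C agitation and aggression are tabulated by arm (SAP 8), so an imbalance would be visible. The trial is descriptive, stopped at 111 of about 432 planned subjects, and no decision rule uses this interval.

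All of this stands, and it sets the priority. It does not remove the point. Seeing an imbalance in a table is not the same as adjusting for it. In a plan that reports intervals instead of tests, width and conditional imbalance govern how the result reads. The sign of rho is immaterial to the precision gain.

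**Conclusion.** The point holds as a possible improvement in efficiency and balance, not as an error. The model lacks a baseline severity term, and a suitable covariate is complete in the analysis set. Adding it costs about 0.5% in interval width at worst and gains about 1.5% to 8% if the absolute correlation lies between 0.2 and 0.4. These figures rest on 37 per arm, complete data and the single-visit approximation. The size of rho is unknown.

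A reader might infer three stronger things that the documents do not support:
- That the planned intervals are certainly too wide. This is so only if the absolute correlation exceeds about 0.10.
- That a baseline imbalance carries over in full. It carries over only in proportion to rho.
- That the unadjusted analysis is biased or invalid. It is unbiased over randomization and its intervals keep their coverage.

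Priority: low.

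**What to change.** Before unblinding:

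1. In SAP 13.3, add Baseline CMAI total score and its interaction with visit to the mADCS-CGIC MMRM, matching the structure of the primary model.
2. In SAP 12.2, replace the bare exception for mADCS-CGIC with a statement that Baseline CMAI total score is its baseline covariate.
3. In SAP 19, which now lists no changes, record the departure from the model in Protocol 9.6.3 and the synopsis.

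If the sponsor prefers to keep the protocol model as the lead result, the adjusted model can be shown beside it.

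The cost is at most 4 model degrees of freedom: one slope plus three interaction terms over four visits. No new data are needed, and no subject is lost, because Full Analysis Set membership already requires the covariate.
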